5.3. INTENT-TO-TREAT [ITT] POPULATION

All patients who take at least one dose of study medication and have evaluable pH monitoring data for at least 1 hour post-dosing will be included into intent-to-treat (ITT) population.

5.4. PER PROTOCOL [PP] POPULATION

The inclusion/exclusion from per protocol (PP) population will be confirmed during data review meeting, but will include patients who satisfied following criteria and did not experience any major protocol violations in ITT population: patients who adhered to the inclusive/exclusive criteria; did not take any prohibited medication which would interfere with evaluation of drugs in the study period; attended visits within the specified visit windows and had complete pH monitoring data for 4 hour post-dosing for both pH monitoring visits.

A major violation of the protocol is defined as any violation of the protocol that is considered to affect the efficacy results and may include the following:

- When a randomization error or administration of the wrong study medication occurred;
- When the patient did not satisfy the inclusion/exclusion criteria;
- When the patient had taken prohibited concomitant medications;
- When the patient failed to attend visit at specified visit windows;
- When the efficacy (4 hour post-dosing monitoring) evaluation was not completed for either monitoring visits.

Protocol violations will be categorized before database lock and will be summarized (by treatment sequence group and overall) and listed.

6. GENERAL CONSIDERATIONS

6.1. REFERENCE START DATE AND STUDY DAY

Study Day will be calculated from the reference start date, and will be used to show start/stop day of assessments and events.

Reference start date (Day 0) is defined as the day of first dose of study medication.

Document: Reckitt Benckiser GA1202 Statistical Analysis Plan

Author: [REDACTED]

Version Number:

Final 5.1

Version Date:

[25Feb2014]

Template No: CS_TP_BS016 – Revision 3

Effective Date: 01May2012

Reference: CS_WI_BS005

Page 10 of 29

- Study Day = (date of event – reference start date).

In the situation where the event date is partial or missing, Study Day, and any corresponding durations will appear partial or missing in the listings.

Randomization date will be considered as the same date of randomization visit, that is, visit 2.

6.2. BASELINE

Unless otherwise specified, baseline value refers to the tests or measurements recorded at Visit 1, screening visit. If a particular test or measurement was repeated after Visit 1, screening visit, then the baseline value is defined as the last non-missing measurement taken prior to Visit 2, Day 0 (including unscheduled assessments). In the case where the last non-missing measurement and the reference start date coincide, that measurement will be considered pre-baseline, but Adverse Events (AEs) and medications commencing on the reference start date will be considered post-baseline.

For patients randomized but not treated, baseline is defined as the last non-missing measurement taken on or before the baseline visit date.

6.3. RETESTS, UNSCHEDULED VISITS AND EARLY TERMINATION DATA

In general, for by-visit summaries, data recorded at the nominal visit will be presented. Unscheduled measurements will not be included in by-visit summaries. In the case of a retest (same visit number assigned), the latest available measurement for that visit will be used for by-visit summaries.

Early termination data will be mapped to the next available visit number for by-visit summaries.

Listings will include scheduled, unscheduled, retest and early discontinuation data.

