16.4 LABORATORY EVALUATIONS

Clinical assessments on hematology and clinical chemistry are to be measured at Visit 1 and Visit 3 (Early Termination Visit). A list of laboratory assessments to be included in the outputs is provided in appendix 1.

Local laboratories will be used for the assessment of hematology and clinical chemistry data and these data will be converted to the International System (SI) of units by Data Management Team using standard conversion factors. Quantitative laboratory measurements reported as “ $< X$ ”, i.e. below the lower limit of quantification (BLQ), or “ $> X$ ”, i.e. above the upper limit of quantification (ULQ), will be converted to X for the purpose of quantitative summaries, but will be presented as recorded, i.e. as “ $< X$ ” or “ $> X$ ” in the listings.

At each visit, summary statistics for the absolute laboratory value and the changes from baseline will be presented by treatment sequence group and overall. The significance of changes from baseline will be assessed using the Wilcoxon Signed-Rank Test within each sequence group and overall.

Each pre-study baseline laboratory value will be categorised as low, normal, or high based on the reference range:

Low: Below the lower limit of the laboratory reference range.

Normal: Within the laboratory reference range (upper and lower limit included).

High: Above the upper limit of the laboratory reference range.

Each post-baseline value will be classified in a similar manner, producing a 3×3 table for each treatment sequence group at each post-baseline visit. Scores of “1” will be assigned to low values, “2” to normal values, and “3” to high values. Using these scores, shifts from baseline will also be assigned a score. For example, a laboratory value that shifts from low to high will be assigned a score of 2, whilst a laboratory value that remains at a low value will be assigned a score of 0. Shifts between these categories between baseline and Visit 3 (Early Termination Visit) will be compared using the Wilcoxon Signed-Rank test within each treatment sequence group and overall. Statistical testing will be performed at last visit.

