In addition to the high and low quantitative laboratory assignments (as identified by means of the laboratory reference ranges), clinically significant quantitative laboratory assessments will be identified by investigator and the result will be recorded in the CRF. The number and percentage of patients with abnormal or clinically significant results will be tabulated by treatment sequence groups by visit. The results will also be listed.

Women of child-bearing potential will undergo urine pregnancy testing (positive or negative). The results will be listed.

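### A normal retest under the same visit number replaces an abnormal Visit 3 laboratory value in the by-visit tables, and no worst-value table is planned to keep it in view

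*SAP*

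**What the plan says.** SAP 6.3 sets the default for by-visit output: "In general, for by-visit summaries, data recorded at the nominal visit will be presented". It then gives two special rules. For repeats under one visit number: "In the case of a retest (same visit number assigned), the latest available measurement for that visit will be used for by-visit summaries". For other extra samples: "Unscheduled measurements will not be included in by-visit summaries". On listings it adds: "Listings will include scheduled, unscheduled, retest and early discontinuation data".

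SAP 16.4 fixes the time points: "Clinical assessments on hematology and clinical chemistry are to be measured at Visit 1 and Visit 3 (Early Termination Visit"). Its outputs follow the visit structure: "At each visit, summary statistics for the absolute laboratory value and the changes from baseline will be presented by treatment sequence group and overall"; "The number and percentage of patients with abnormal or clinically significant results will be tabulated by treatment sequence groups by visit". On shifts: "Shifts between these categories between baseline and Visit 3 (Early Termination Visit) will be compared using the Wilcoxon Signed-Rank test". SAP 16.4 does not set SAP 6.3 aside. The SAP list of tables (14.3.3.1 to 14.3.3.10) contains no worst-value or any-time-after-dosing laboratory table.

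Baseline has its own rule in SAP 6.2, which takes the last non-missing measurement before Visit 2.

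**The concern.** Taking the latest value is sensible at baseline, where the aim is the state just before treatment. After dosing, a safety table should show whether an abnormality occurred. Under SAP 6.3 a Visit 3 abnormality can be overwritten by a later sample.

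Three features of this trial make that more than a formality.

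- There is one scheduled post-baseline laboratory time point, so no other scheduled value can show the abnormality.
- Protocol 11.3.2.2 places the Visit 3 blood sample after pH monitoring on the same day, when all dosing is finished. A repeat is further from exposure than the protocol-timed sample, yet the rule prefers the repeat.
- Protocol Section 6 names raised plasma sodium and hypercalcaemia among the product's possible reactions, and Protocol 13.4 measures both analytes.

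At stake are the abnormal and clinically significant counts, the shift tables and the related tests. The primary endpoint is not touched.

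**Working it through.** The plan states no figure on this point, so there is none to reproduce. The check traces the rule through the possible cases and then asks how much one replaced value can matter.

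**Step 1. Which value enters the by-visit tables under SAP 6.3?**

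| Case | Visit 3 sample | Further sample | Value used | Effect on tables |
|---|---|---|---|---|
| a | high | retest, same visit number, normal | normal | abnormality leaves |
| b | high | recheck coded unscheduled, normal | high | abnormality stays |
| c | normal | unscheduled visit only, high | normal | abnormality never enters |
| d | normal | retest, same visit number, high | high | abnormality added |

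A same-visit retest that is still high also stays in. Only case (a) removes an abnormal Visit 3 result. Cases (a) and (b) can describe the same blood results and differ only in how the second sample is coded. Case (c) is a separate gap: Protocol 11.6 allows clinical assessments at unscheduled visits, but a value from one reaches no laboratory summary.

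**Step 2. Which outputs does case (a) affect?** Observed values (Tables 14.3.3.1, 14.3.3.3), change from baseline (14.3.3.2, 14.3.3.4), abnormal results (14.3.3.5, 14.3.3.6), clinically significant results (14.3.3.7, 14.3.3.8) and shifts (14.3.3.9, 14.3.3.10). The signed-rank tests are affected if they use the by-visit value. SAP 6.3 speaks only of summaries, and SAP 16.4 names no other value for the tests.

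Both SAP 16.4 and Protocol 14.5.2 say that every post-baseline value is to be put into a low, normal or high category. SAP 6.3 carries only one value per visit forward. The two sit uneasily together, although one shift table per visit can be read as implying one value per visit.

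**Step 3. Size per affected patient.** Each case (a) patient lowers the count by one. The plan expects 44 enrolled and 36 evaluable. Taking these as the range for the denominator (an assumption, since the tables use the Safety Population):

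- overall: 1/44 = 2.3% to 1/36 = 2.8%;
- per sequence group, if the groups are equal (also assumed): 1/22 = 4.5% to 1/18 = 5.6%.

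**Step 4. Effect on a shift test (illustration; the counts are assumed).** SAP 16.4 scores low, normal and high as 1, 2 and 3, so a normal-to-high shift scores 3 − 2 = 1 and no change scores 0. If k patients shift one category in the same direction and zeros are dropped, the exact two-sided signed-rank p-value is 2 × (1/2)^k.

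| k | p |
|---|---|
| 4 | 0.125 |
| 5 | 0.063 |
| 6 | 0.031 |
| 7 | 0.016 |

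With six shifts, replacing one by a normal retest moves p from 0.031 to 0.063. One value can cross the 5% level in SAP 6.4, provided the test uses the by-visit value.

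**The case against.** The strongest reply is that this is a pre-specified, neutral convention that affects supportive tables only. Much of it stands.

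- **Unscheduled samples.** A reader might infer that both rules in SAP 6.3 erase re-checked abnormal results. They do not. If the recheck is coded unscheduled, the recheck is dropped and the abnormal value stays (case b). Visit 3 is the last scheduled visit, so a later attendance may well be coded that way. The protocol schedules no laboratory retest, so case (a) may never occur.
- **Direction.** A reader might infer a one-way bias. As worded, the rule works in either direction (case d) and also covers repeats of unusable samples. A net shift towards normal requires that retests mostly follow abnormal results. That is a reasonable inference but is not stated.
- **Visibility.** A reader might infer that the abnormality vanishes from the report. Listings keep all values, and clinically significant results have their own listings (16.2.6.2, 16.2.6.4). Protocol 13.1.4 lets a significant laboratory abnormality be recorded as an adverse event. The window in SAP 16.2, up to one day after the last IMP dose, covers the Visit 3 sample, so such an event reaches the adverse event tables. Listings are not counts, however, and an abnormality not judged significant need not become an event.
- **Sodium and calcium.** Protocol Section 6 ties the calcium effects to high doses and the sodium effect especially to renal and cardiovascular patients on salt restriction. Protocol 10.2 excludes known hypercalcaemia, impaired heart or kidney function and patients needing a low-sodium diet. Group A receives placebo at Visit 3, with NIMP stopped 24 hours earlier. A transient effect missed in that group would be due to the sampling schedule, not to the retest rule.

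What the reply does not answer is that, where case (a) occurs, the plan has no laboratory table that counts the patient as abnormal, and that the coding of the second sample decides the result.

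**Conclusion.** The point holds in conditional form. Two things must coincide: the retest carries the Visit 3 number, and the latest value is normal. The abnormality then leaves every by-visit laboratory table, and also the signed-rank tests if they use the same value. A mainly downward effect on abnormal counts rests on the inference about why retests are ordered. The number of patients affected cannot be derived from the documents. The percentages per patient and the p-values above show sensitivity; they do not predict an effect.

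Separately, an abnormality seen only at an unscheduled visit is in no laboratory summary. The documents do not support a claim that re-checked results are lost in general, or that the report would hide them. This is a modest weakness in secondary safety reporting that is worth correcting because the correction is cheap.

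**What to change.** Amend SAP 6.3 and 16.4 as follows.

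1. Keep the latest-value rule for baseline, as SAP 6.2 already provides.
2. For Visit 3 or Early Termination, use the first technically valid sample for observed values and change from baseline. Replace it only if the laboratory rejected the sample.
3. Base the abnormal, clinically significant and shift tables on the worst post-dose value, including retests and unscheduled samples. For analytes with a lower and an upper limit, define what counts as worst in each direction. At minimum, leave these tables as they are and add one worst-post-dose table.
4. State which value the signed-rank tests use. The first valid sample avoids choosing a value by its result.

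Visit 3 and Early Termination can remain pooled, because Protocol 14.5.2 defines the last visit that way.

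The cost is a few sentences and minor programming, and abnormal counts may be slightly higher. If the SAP can no longer be revised, the extra table could be added through a change form of the kind used in July 2014 to add the listing of minor deviations.

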6.4. STATISTICAL TESTS

The default significant level will be (5%); confidence intervals (CIs) will be 95% and all tests will be two-sided, unless otherwise specified in the description of the analyses.

6.5. COMMON CALCULATIONS

For quantitative measurements, change from baseline will be calculated as:

- Test Value at Visit X – Baseline Value

Log transformed (natural logarithm) of efficacy data (or another transformation) might be used in the statistical models if after inspection of the data it is considered necessary. This decision will be undertaken in collaboration with the sponsor.

Document: Reckitt Benckiser GA1202 Statistical Analysis Plan

Author: [REDACTED]

Version Number:

Final 5.1

Version Date:

[25Feb2014]

Template No: CS_TP_BS016 – Revision 3

Effective Date: 01May2012

Reference: CS_WI_BS005

Page 11 of 29

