14.4.3 Statistical Methods for Efficacy Analyses

SAS 9.1 (or later) will be used for statistical analysis.

All statistical tests will be conducted using two-tailed tests at the 5% significance level.

The null hypothesis at all times will be the equality of the fixed effect being compared from the model.

The primary endpoint will be analysed primarily using an ANOVA of variance model with treatment, dosing visit treatment sequence as fixed effects and patient nested within treatment sequence as a random effect. The difference between treatment least square means will be used to represent the treatment differences. The effects for dosing visit and treatment sequence will also be assessed. A residual analysis will be performed. If there is a major departure from the assumptions of normality, independence or heteroscedasticity of residuals, then further analysis using transformed data will be used to support the original model results. If such assumptions still do not hold following an appropriate transformation then Wilcoxon Rank-Sum test will be used to compare the dosing visit difference (dosing visit 1 – dosing visit 2) between treatment sequence groups to represent the treatment comparison.

All secondary endpoints will be analysed identically to the primary endpoint.

All secondary endpoints and sensitivity or alternate analyses for the primary endpoint will serve as supportive evidence for the primary analysis only and therefore no adjustment for multiple comparisons will be made.

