15.1.3 PRIMARY ANALYSIS OF PRIMARY EFFICACY VARIABLE

The primary endpoint will be analysed primarily using a linear mixed model with treatment, dosing visit and

Document: Reckitt Benckiser GA1202 Statistical Analysis Plan

Author: [REDACTED]

Version Number:

Final 5.1

Version Date:

[25Feb2014]

Template No: CS_TP_BS016 – Revision 3

Effective Date: 01May2012

Reference: CS_WI_BS005

Page 16 of 29

treatment sequence as fixed effects and patient nested within treatment sequence as a random effect. The primary analysis is to test the null hypothesis that there is no difference between treatment, Least square means (with 95% CI) corresponding to the two treatments will be presented. Descriptive statistics will also be presented for the primary endpoint by treatment for each dosing visit and overall. The effects for dosing visit and treatment sequence will also be assessed.

The following SAS core code will be used.

```
proc mixed data=XXX method=REML;
  class treatment visit sequence subID;
  model Y= treatment visit sequence /ddf=kenwardroger;
  random subID(sequence);
  lsmeans treatment/diff cl;
run;
```

SAS output from Mixed procedure will be sent to the sponsor to assist with the model assumptions review.

The linear mixed model for the primary endpoint is based on the assumption that the percentage of time with pH<4 within each treatment sequence group is normally distributed. To test this assumption, a qualitative residual analysis will be performed. If there is a major departure from the assumptions of normality or heteroscedasticity of residuals, then further analysis using transformed data might be performed if deemed necessary. If the analysis based on the transformed data still rises reasonable concerns about validity of the tests then the Wilcoxon Rank-Sum test will be used to compare the dosing visit difference (dosing visit 1 – dosing visit 2) between treatment sequence groups to represent the treatment comparison.

The primary efficacy analysis will be performed for the ITT population using adjusted 4-hour data based on the imputation rule specified in section 15.1.2.

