15.2.2 MISSING DATA METHODS FOR SECONDARY EFFICACY VARIABLES

Missing data for the percentage of time during the 4 hour post dosing period with pH below pH 5 due to early termination of recording will be derived in the same way as for the primary efficacy variable.

For the following secondary efficacy variables:

- Number of occasions during the 4 hour post dosing period when pH falls below pH 4
- Number of occasions during the 4 hour post dosing period when pH falls below pH 5
- Number of reflux episodes during the 4 hour post dosing period with pH below pH 4 for at least 5 minutes

If less than 2 hours post-dosing monitoring result for these variables is available, for whatever reason, the derived variable will be considered missing. If 2 or more hours post-dosing pH data is available then the variable will be multiplied by 4 / (hours of post-dosing pH data available). Any data recorded more than 4 hours post-dosing will be ignored when deriving these parameters.

The table below shows the implementation of adjustment rules (take number of occasions as an example) under different monitoring duration scenarios.

Monitoring Duration(End of pH monitoring – taking treatment)	Number of occasions with pH<4 during the monitoring period (data directly from database)	Adjustment factor	Adjusted occasion with pH<4 over 4 hours
240 mins (4 hours)	2	1	2
230 mins (<4 hours)	2	240/230	2*240/230=2.09
90 mins (<2 hours)	1	NA	missing

Missing data for other secondary endpoints due to early termination of recording will not be derived.

Document: Reckitt Benckiser GA1202 Statistical Analysis Plan

Author:

Version Number:

Final 5.1

[25Feb2014]

Template No: CS_TP_BS016 – Revision 3

Effective Date: 01May2012

Reference: CS_WI_BS005

Page 18 of 29

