15.2.3 ANALYSES OF SECONDARY EFFICACY VARIABLES

The analysis methods for all secondary endpoints will be identically to those described for the primary endpoint in 15.1.3.

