17 LIST OF TABLES

- 14.1.1 Patient Disposition and Withdrawals – All Patients
- 14.1.2 Protocol Deviations/Violations – Full Analysis Set
- 14.1.3 Summary of Patiens Excluded from Analysis Populations – Full Analysis Set
- 14.1.4 Demographic and Baseline Characteristics – Full Analysis Set
- 14.1.5 Smoking habits and Alcohol/Drug Use – Full Analysis Set
- 14.1.6 GERD Status at Baseline – Full Analysis Set
- 14.1.7 12-Lead ECG Examination – Full Analysis Set
- 14.1.8 Endoscopy Examination – Full Analysis Set
- 14.1.9.1 Medical History – Full Analysis Set
- 14.1.9.2 Concomitant Illnesses – Full Analysis Set

Document: Reckitt Benckiser GA1202 Statistical Analysis Plan

Author:

Version Number:
Version Date:

Final 5.1
[25Feb2014]

Template No: CS_TP_BS016 – Revision 3

Effective Date: 01May2012

Reference: CS_WI_BS005
Page 23 of 29

- 14.1.10.1 Prior Medications and Therapies - Full Analysis Set
- 14.1.10.2 Concomitant Medications and Therapies – Full Analysis Set
- 14.1.11 NIMP Accountability – Safety Population
- 14.1.12 4-Hour Monitoring Procedure – Intent-to-treat Population

- 14.2.1.1 Summary of 4-hour pH Monitoring Results based on Adjusted 4-hour Data – Intent-to-treat Population
- 14.2.1.2 Summary of 4-hour pH Monitoring Results based on Adjusted 4-hour Data by Center – Intent-to-treat Population

- 14.2.2.1 Analysis of Treatment Difference during the 4-hour Post Dosing Period based on Adjusted 4-hour Data – Intent-to-treat Population
- 14.2.2.2 Analysis of Treatment Difference during the 4-hour Post Dosing Period – Per protocol Population
- 14.2.2.3 Analysis of Treatment Difference during the 4-hour Post Dosing Period based on Log Transformed Adjusted 4-hour Data – Intent-to-treat Population

- 14.2.3.1 Analysis of Visit and Sequence Difference during the 4-hour Post Dosing Period – Intent-to-treat Population
- 14.2.3.2 Analysis of Visit and Sequence Difference during the 4-hour Post Dosing Period – Per Protocol Population

- 14.3.1.1 Summary of All Adverse Events – Safety Population
- 14.3.1.2 Comparison of Adverse Events during the 4-hour Post Dosing Period – Safety Population
- 14.3.2.1 Overall Adverse Events by System Organ Class, Preferred Term and Intensity – Safety Population
- 14.3.2.2 Overall Related Adverse Events by System Organ Class, Preferred Term and Intensity – Safety Population
- 14.3.2.3 Overall Serious Adverse Events by System Organ Class, Preferred Term and Intensity – Safety Population

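### Does the log-transformed analysis need a written rule for endpoints that can be exactly 0?

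*SAP*

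**What the plan says.** SAP 6.5 (Common Calculations) states that "Log transformed (natural logarithm) of efficacy data (or another transformation) might be used in the statistical models" if inspection of the data shows a need, with the decision taken together with the sponsor. The natural log is the only transformation named, but the wording leaves room for others.

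SAP 15.1.3 fits a linear mixed model to the untransformed primary percentage and reviews the residuals. If there is a major departure, a transformed analysis may follow. The Wilcoxon rank-sum test on visit differences comes next: "If the analysis based on the transformed data still rises reasonable concerns about validity of the tests". Protocol 14.4.3 has the same ladder ("If such assumptions still do not hold following an appropriate transformation"). It adds that the transformed analysis supports the original model, and that secondary endpoints and alternative analyses are supportive only.

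SAP 15.2.3 carries this over: "The analysis methods for all secondary endpoints will be identically to those described for the primary endpoint in 15.1.3". The secondary endpoints include "Number of reflux episodes during the 4 hour post dosing period with pH below pH 4 for at least 5 minutes". Under SAP 15.2.2, when a recording is short but lasts at least 2 hours, "then the variable will be multiplied by 4 / (hours of post-dosing pH data available").

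The list in SAP 17 has one transformed output, Table 14.2.2.3: "Analysis of Treatment Difference during the 4-hour Post Dosing Period based on Log Transformed Adjusted 4-hour Data – Intent-to-treat Population". Neither document gives an offset or any other rule for a value of 0.

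**The concern.** Percentages of time and counts of reflux events can both be exactly 0. Entry to the trial rests on symptoms (Protocol 11.3.1.1), so no minimum acid exposure is guaranteed. A plain natural log would turn zero sessions into missing values.

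Those sessions are the best outcomes. If they are more common on active treatment, an analysis that loses them describes only sessions with some reflux, while its title still says intent-to-treat. A treatment that abolishes episodes altogether would show less of its effect there. The study is open-label and the choice of transformation waits for the data, so a rule fixed in advance looks like a cheap safeguard.

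**Working it through.** **1. The adjustment leaves zeros alone.** The worked examples in the SAP reproduce: 2 × 240/230 = 2.09 occasions (15.2.2), and 230 × 80% × 240/230 / 240 = 80.0% (15.1.2). By the same formula, 0 × 240/230 = 0.

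**2. When the 5-minute count must be 0.** One qualifying episode needs 5 of 240 minutes: 5/240 = 2.08%. Any full session below that percentage has a count of 0. This follows from the definitions alone, but it does not say how often it happens.

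**3. How often it might happen.** The documents give no exposure data, so the inputs are assumed: log-normal percentage, between-patient log SD 0.9, within-patient log SD 0.5 to 0.9, active/placebo ratio 0.5 to 0.7. The total SD is √(0.81 + 0.25) = 1.03 up to √(0.81 + 0.81) = 1.27. The minimum zero share is Φ[ln(2.083/median)/SD]. For a placebo median of 5% and SD 1.03 this is Φ(−0.876/1.03) = Φ(−0.85) = 20%. The last column uses the matching bivariate normal probability.

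| Placebo median | Placebo zeros, at least | Active zeros, at least | Patients of 36 non-zero at both visits, at most |
|---|---|---|---|
| 2% | 51–52% | 62–76% | 8–11 |
| 5% | 20–25% | 31–44% | 18–23 |
| 10% | 6–11% | 12–25% | 26–31 |

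The answer runs from a small nuisance to most sessions, depending on a median that nobody can read from the documents.

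**4. Cost for a count if zeros were dropped.** Simulated two-period crossover, 36 patients, Poisson counts with a gamma patient multiplier (variance 0, 0.5 or 1), true ratio 0.5. The mixed model has treatment, visit, sequence and random patient, and keeps unpaired sessions, as SAP 15.1.3 does. Its degrees of freedom were bracketed in place of Kenward-Roger.

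| Placebo mean | Log, zeros dropped: power | Untransformed: power | Log, zeros dropped: ratio |
|---|---|---|---|
| 1 | 15–26% | 63–69% | 0.79–0.84 |
| 2 | 54–68% | 90–93% | 0.69–0.71 |
| 4 | 89–99% | 99–100% | 0.56–0.60 |

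A simpler paired test on visit differences shows what the permitted alternatives deliver. At mean 1, log(x + 1) has 60–65% and Wilcoxon 58–63%, against 63–66% untransformed and 10–18% for the log with zeros dropped. At mean 8 all four reach 100%. So the loss belongs to one choice, and methods the plan already allows avoid most of it.

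**5. The primary percentage.** Assume a median of 5%, zeros in 10% of placebo and 20% of active sessions, and a paired test.

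| Within SD, ratio | Log, zeros dropped | Square root | Wilcoxon |
|---|---|---|---|
| 0.5, 0.7 | 68% | 62% | 70% |
| 0.9, 0.7 | 28% | 39% | 37% |
| 0.9, 0.5 | 75% | 76% | 78% |

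A second set of assumptions (between- and within-patient log SD 1.0 and 0.8, ratio 0.7) shows that the ranking turns on the zeros. With zeros in 5% of placebo and 20% of active sessions, dropping them gives 36% power, against 69–72% for log(x + c) with c from 0.01 to 1. With 5% zeros in both, dropping gives 40%, against 18–31% for the same offsets.

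**6. Whether a loss would go unseen.** Protocol 14.4 requires n and the minimum by treatment and visit, so a minimum of 0 would appear. Listing 16.2.4.2 shows the pH results for each patient. SAP 15.1.3 sends the mixed-model output to the sponsor for review of assumptions. A log analysis with many sessions missing would be plain in all three places.

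**The case for a change.** The strongest case for a change is that each escape route is optional. Permission to use another transformation supplies no zero rule. The Wilcoxon step waits for concerns about validity, and dropped zeros are not listed as such a concern. Table 14.2.2.3 is a standing output, so a plain log may be run whatever the data look like. If treatment worked only by abolishing reflux, dropping zeros would miss it. With the second set of assumptions in step 5, a ratio of 1 among non-zero values and zeros in 5% of placebo and 20% of active sessions, power is 5% with zeros dropped, against 14% for Wilcoxon and 26–44% for the offsets. One sentence would cost little.

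What stands is that the rule is missing and that a plain log would suit a low count badly. The rest is weaker. No text tells anyone to discard an observed 0. Protocol 14.4.3 asks for an appropriate transformation, and a log undefined for many sessions is hard to call that. Harm needs a chain: a plain log with no offset, used on an endpoint with many zeros, with no one acting on the visible loss and Wilcoxon not used. Which endpoints Table 14.2.2.3 covers depends on templates that are not among the documents.

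A rule also has its own risk, since a fixed small offset can do worse than dropping zeros. For a count with placebo mean 8, high patient variation and ratio 0.7, power is 53% at c = 0.1 against 79% with zeros dropped. Sending every endpoint with a zero straight to Wilcoxon gives up the ratio estimate.

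**Conclusion.** No change is needed. This is missing detail in a supportive analysis, of a kind that analysts fill sensibly when they meet it. The primary conclusion rests on the untransformed mixed model, which uses every zero, and the rank test behind it is defined at 0 as well.

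The possible damage is confined to a supportive table. It ranges from nearly nothing (counts averaging four or more) to a largely uninformative result (counts averaging one), and that only if a plain log were used without an offset. The zero shares, count means and variances behind these figures are all assumptions. For the primary percentage the direction of the effect is not fixed, so no loss is claimed there, and no single zero rule would be a clear gain across the endpoints. When the log analysis is run, ordinary good practice is enough: report how many sessions are 0 by treatment, and use one of the methods the plan already permits where a log does not fit.
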